#### 8.0 STATISTICS

## 8.1 Determination of Sample Size

Part 1 includes a sample size with 100 subjects, in which 20 patients are randomized each to 1.5 mg HS, 1.5 mg BID, 3 mg HS, 3 mg BID, and placebo in the ratio 1:1:1:1:1. See also the discussion of randomization in Section 4.1.5.2.

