## 8.1.1 Expected Number of Subjects by Part

The following assumptions were used:

- The 1:1:1:1 (1.5 mg HS: 1.5 mg BID: 3 mg HS, 3 mg BID: placebo) randomization ratios will remain constant throughout the study.
- Based on these randomization ratios, approximately 80% of all subjects in Part 1 will be treated with an APT-1011 dosing regimen and approximately 20% of all subjects in Part 1 will be treated with placebo.
- Based upon the PR-021 study, which had slightly different histologic response criteria, it is expected that approximately 60% of patients on active treatment are expected to be a histologic responder compared to 10% on placebo. The lowest dose may be less effective.
  - Assuming a 60% histologic response rate for the 3 highest active doses of 1.5 mg BID, 3 mg HS, 3 mg BID, a 20% response rate for 1.5 mg HS, and a 10% response rate for placebo, it is expected that overall approximately 50% of active treatment will be responders at Week 12 (40 out of 80).
  - o It is expected that at Week 26 an additional 20% will drop out who were previously responders and of the PART 1 non-responders that 40% will still be non-responders.
  - After Week 26, of the remaining subjects, it is expected that approximately 20% will dropout before Week 52.

Given these assumptions, it is expected that approximately 42 patients will be responders and complete Week 26, and about 34 of those responders will complete Week 52.

The power for testing each active dose versus placebo given a histologic response rate of 60% active treatment and 10% placebo for the primary endpoint (Part 1) is equal to 97.5% (one-sided Type I error = 0.05). Additionally, the power for achieving statistical significance for all 3 of the highest active doses of 1.5 mg BID, 3 mg HS, 3 mg BID via the gatekeeping hypothesis testing approach assuming independence is approximately 0.93.

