- Odds ratios will be provided per 1.5 mg increase in dose and per 1 unit increase in daily dose frequency. 3 mg doses will be coded as 2, 1.5 mg doses will be coded as 1, and placebo will be coded as 0. For frequency, BID will be coded as 2, and HS will be coded as 1. The variables will be analyzed in continuous form, but re-coding in this way will allow for provision of the odds ratios per 1.5 mg increase.
- o If the dose-frequency interaction term is significant at the 10% level, separate logistic regression analyses models will be fitted for each dose level separately, with dose frequency in the model (and repeated with the randomization strata also in the model). If the interaction term is not significant, a model without the interaction terms will be used to estimate the effects of dose and frequency
- The primary efficacy variable will be summarized for each subgroup defined in section 7.5, by each of the five randomized dosing groups.
 - For the dose with maximum utility (i.e. largest effect size), logistic regression will be used to estimate Odds ratio of APT-1011 vs Placebo within each subgroup
 - For other doses, no statistical testing will be performed for results within each subgroup.

All these secondary analyses of the primary efficacy variable will be performed on the FAS analysis set.

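### Subgroup odds ratios are planned only for the dose with the largest effect; if the three highest doses are equally effective as planned, that dose's response rate is overstated by about 9 points on average

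*SAP*

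**What the plan says.** SAP section 16.1.5 sets out the subgroup work in three steps. First, all arms are tabulated: "The primary efficacy variable will be summarized for each subgroup defined in section 7.5, by each of the five randomized dosing groups". Second, one dose gets an effect estimate within each subgroup: "For the dose with maximum utility (i.e. largest effect size), logistic regression will be used to estimate Odds ratio of APT-1011 vs Placebo". Third, the rest do not: "For other doses, no statistical testing will be performed for results within each subgroup".

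The SAP does not give the scale on which effect size is judged, a rule for ties, or whether the dose is picked once overall or again within each subgroup. Section 7.4 classes all testing outside the gated primary analysis and the dysphagia analysis as descriptive. Section 7.5 warns that power within subgroups is limited.

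Protocol section 8.8.3 plans subgroup analyses without limiting them to one dose. Protocol section 2.5 states that 3 mg HS was chosen for future development on the balance of efficacy and safety and on convenience.

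**The concern.** When several doses are compared with the same placebo arm and the best-looking one is chosen, its result contains both its true effect and the chance variation that put it first. Estimating its effect from the same data, without correction, gives an answer that is too favourable on average. The closer the true effects, the more the choice rests on chance, and the protocol plans on three doses being equal.

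Two things follow. The only planned subgroup odds ratios would come from a dose favoured by selection. The remaining doses would have raw response rates by subgroup but no comparison with placebo and no interval. The rule follows the largest effect, whereas the development dose was chosen on other grounds, so that dose may be among those left out.

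**Working it through.** **Inputs.** Protocol section 8.1: "20 patients are randomized each to 1.5 mg HS, 1.5 mg BID, 3 mg HS, 3 mg BID, and placebo in the ratio 1:1:1:1:1". Protocol section 8.1.1: "Assuming a 60% histologic response rate for the 3 highest active doses of 1.5 mg BID, 3 mg HS, 3 mg BID", and "a 20% response rate for 1.5 mg HS, and a 10% response rate for placebo".

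**The plan's own figure first.** Power for 60% v 10%, 20 per arm, one-sided 0.05, pooled variance under the null and no continuity correction:
- average rate = (0.6 + 0.1)/2 = 0.35; null SE = √(2 × 0.35 × 0.65/20) = 0.1508
- alternative SE = √(0.6 × 0.4/20 + 0.1 × 0.9/20) = 0.1285
- power = Φ[(0.5 − 1.645 × 0.1508)/0.1285] = Φ(1.96) = 0.975
- all three highest doses, treated as independent: 0.975³ = 0.927

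These match the stated 97.5% and approximately 0.93. The documents give no figure for selection bias.

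**Selection bias on the rate scale.** Placebo is common to all comparisons, so picking the largest unadjusted rate difference is the same as picking the largest response rate. For independent binomial counts X₁ to X₄, P(max ≤ k) = ∏ P(Xⱼ ≤ k), which gives E[max] exactly.
- At 60/60/60/20%, E[max] = 13.83 responders out of 20, or 69.2%.
- Bias = 69.2 − 60 = 9.2 points.
- 1.5 mg HS is almost never selected, and each of the other three is selected in about one third of trials. Two or more doses tie for the largest rate in about 18% of trials.

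**Sensitivity.** The unequal rates below are assumptions for illustration (400,000 simulated trials each). Bias is the selected dose's observed rate minus its own true rate.

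| True rates, four doses (%) | Mean bias (points) |
|---|---|
| 60/60/60/60 | 11.1 |
| 60/60/60/20 (planning) | 9.2 |
| 65/60/55/20 | 8.3 |
| 70/60/50/20 | 6.1 |
| 75/60/50/20 | 4.4 |
| 80/60/50/20 | 2.6 |
| 90/60/60/20 | 0.7 |

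**Within subgroups.** If the dose is picked once overall and both levels have a true rate of 60%, each level carries the same 9.2 points on average (checked at splits of 15:5, 10:10 and 19:1). If the levels differ (50% in 15 subjects, 90% in 5), the biases are 10.3 and 3.4 points. If the dose were picked afresh in each subgroup, the bias at the planning rates would be 12.8 points with 10 per arm and 17.9 with 5 per arm.

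**Odds-ratio scale.** Whole arm, planning rates, 0.5 added to each cell: the mean log odds ratio is 2.584 for a dose fixed in advance and 2.969 for the selected dose. The geometric means are exp(2.584) = 13.2 and exp(2.969) = 19.5, and the factor is exp(0.385) = 1.47.

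**Whether the subgroup odds ratio exists.** Expected placebo responders = 20 × 0.10 = 2. With none in a subgroup level, maximum-likelihood logistic regression gives no finite odds ratio. P(at least one in both levels) = (1 − 0.9ᵃ)(1 − 0.9ᵇ):
- 10:10 split: 0.651 × 0.651 = 0.42
- 14:6 split: 0.771 × 0.469 = 0.36
- 15:5 split: 0.794 × 0.410 = 0.33

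**The case against.** **The size depends on assumptions.** A reader might infer that every subgroup estimate is 9 points too favourable. The documents do not support that. The figure is an average that needs three equal doses at 60%. SAP section 16.1.3 expects higher doses to do better, which would shrink it, and it differs between subgroups whose true rates differ. In a 10-of-20 subgroup at the planning rates, the selected dose's observed rate is still below the truth in about 14% of trials. This stands.

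**Scale.** The planned estimate is an odds ratio, so percentage points are not its scale. The factor of 1.47 is a whole-arm figure with a continuity correction, not the planned subgroup estimator. This stands; both numbers indicate size only.

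**Other doses are not invisible.** A reader might infer that they have no subgroup results at all. They do: response rates in all five arms are tabulated at every level, free of selection. What is missing is the comparison with placebo and its interval.

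**Comparison between levels.** If the dose is picked once and true rates are equal across levels, the inflation is the same at each level on the rate scale, so the contrast between levels is not distorted on average. This is correct under those conditions.

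**Sparse placebo responders** would trouble a dose fixed in advance just as much, and a single 10-subject level has at least one placebo responder in 65% of trials. It is a separate weakness, but the same change in reporting deals with it.

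**Descriptive status.** The label limits the consequences. It does not remove bias from the only subgroup effect estimate that is planned.

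**Conclusion.** The point holds in conditional form. Under the protocol's planning rates, the rule overstates the selected dose's response rate by about 9 points on average and its whole-arm odds ratio by a factor of about 1.5. The bias is about 8 points to under 1 in the illustrative cases where doses differ, and about 11 points if all four are equal at 60%. This rests on 20 subjects per arm, selection on the observed unadjusted effect, and one selection overall. That the effect is the observed one is the natural reading; the SAP does not say so.

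A reader might infer that the primary result is compromised. It is not: the gated tests in SAP section 16.1.3 cover all four doses in a fixed order and do not use this selection. Nor do the documents show that the rule influenced the choice of 3 mg HS. What is affected is a descriptive secondary analysis, which would give its only subgroup effect estimates for a dose favoured by chance and might give none for the dose taken forward. The change is worth making because it is cheap.

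**What to change.** In SAP section 16.1.5, delete the maximum-utility selection and the sentence that excludes the other doses. For every subgroup level and all four doses, report the responder-rate difference from placebo with a 90% score interval, labelled descriptive. This removes the selection, leaves no need for a tie rule or a definition of effect size, and gives an interval even when a cell is zero.

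Naming a single dose in advance would also remove the selection, but it is a weaker choice. The first hypothesis in the gate is 3 mg BID, while Protocol section 2.5 takes 3 mg HS forward, so the development dose would still have no estimate.

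The cost is SAP wording and the same code run over four doses, with no new data. Section 7.5 lists 19 subgroup levels (2+2+2+2+4+3+2+2), so there would be 19 × 4 = 76 intervals. Many will be wide: with 5% of subjects expected to be 65 or older, that level has about 20 × 0.05 = 1 subject per arm.

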16.2. SECONDARY EFFICACY

16.2.1. SECONDARY EFFICACY VARIABLES & DERIVATIONS

16.2.1.1. EoE sustained response: maintenance of ≤6 peak eosinophils/HPF at Weeks 26 and 52 for histologic responders at Week 12

For histologic responders at Week 12, maintenance of ≤ 6 peak eosinophils/HPF at each of Week 26 and Week 52 is defined as having ≤ 6 peak eosinophils/HPF (as per the primary efficacy variable in section 16.1.1), at each of Weeks 26 and 52 respectively.

Subjects who withdrew prior to each of Weeks 26 and 52 will be classified as non-responders at those visits.

Author:

Version Number: 3.0

Version Date: 06NOV2019

Template No.: CS_TP_BS016 Revision 5 Reference: CS_WI_BS005

Page 37 of 70

16.2.1.2. Change from baseline EREFs Total Score at Week 12, Week 26, and Week 52 For total esophagus:

- each of edema and stricture will be classified as either Grade 0 (absent) or Grade 1 (present)
- rings will be classified as Grade 0 (none), Grade 1 (mild), Grade 2 (moderate), Grade 3 (severe)
- each of exudates and furrows will be classified as Grade 0 (none), Grade 1 (mild), Grade 2 (severe)

Crepe paper esophagus and narrow caliber esophagus will each be classified as Grade 0 (absent) or Grade 1 (present).

Esophageal erosions will be classified as Normal, and each of Grade A through to Grade D based on the Los Angeles Classification, but not separately for the proximal and distal esophagus.

A total EREFs score will be derived as follows:

Component	Grade	Score
Edema*	Absent	0
	Present	1
Rings*	Grade 0 (none)	0
	Grade 1 (mild)	1
	Grade 2 (moderate)	2
	Grade 3 (severe)	3
Exudates*	Grade 0 (none)	0
	Grade 1 (mild)	1
	Grade 2 (severe)	2
Furrows*	Grade 0 (none)	0
	Grade 1 (mild)	1
	Grade 2 (severe)	2
Stricture*	Absent	0
	Present	1

Author:

Version Number: 3.0

Version Date: 06NOV2019

Template No.: CS_TP_BS016 Revision 5 Reference: CS_WI_BS005

Page 38 of 70

Crepe paper esophagus	None	0
	Present	1
Narrow caliber esophagus	None	0
	Present	1
Esophageal erosions (Los Angeles	Normal	0
Classification)	Grade A	1
	Grade B	2
	Grade C	3
	Grade D	4
Total score		Sum of the above (ranging from 0
		to 15)

- * For this component the grade/score will be based on the WORST result.
- The change from baseline in the EREFs total score will be summarized as continuous variables, and analysis of covariance (ANCOVA) will be used to compare the mean change from baseline in each of the APT-1011 dosing groups to placebo, at the Week 12 visit, with the estimated mean difference, 90% confidence interval of the mean difference and 1-sided p-values provided. This statistical testing at Week 12 is considered descriptive only and no adjustments will be made for multiple comparisons.
- The ANCOVA models will include the factors described in section 7.1.

•

16.2.1.3. Peak eosinophils/HPF number <1 and <15 at Week 12, Week 26, and Week 52 Subjects who had withdrawn prior to each visit will not have results imputed, and percentages will be based on the number of subjects with EGD results assessed at the visit.

Subjects with a result of <1/HPF will also be counted as having a result of <15/HPF.

- 16.2.1.4. Change from baseline Global EoE Symptom Score at each post-baseline visit The global EoE symptom score, ranging from 0 to 10 will be provided directly to IQVIA Biostatistics with no derivation required. This will be retrieved from the diary.
- 16.2.1.5. Change from baseline in the number of dysphagia episodes at Week 12, Week 26 and Week 52

The number of dysphagia episodes for a subject will be determined from the 14 day evening diary completed prior

Author:

Version Number: 3.0

Version Date: 06NOV2019

Template No.: CS_TP_BS016 Revision 5 Reference: CS_WI_BS005

Page 39 of 70

to each of Week 12, Week 26 and Week 52. The number of episodes for each day will have 2 components a real time episode component along with the CRF entry of the number of dysphadia free days in the last 24 hours. First a day must be identified as a valid day. A day is considered valid if the subject awnsers yes to the CRF question "In the last 24 hours, did you have any difficulty with food or pills going down."

With a valid day from the evening diary the subject will add the real time episode component which comes from the swallowing difficulty. This component is the sum for each day of the CRF question "Did you just experience difficulty with food or pills going down?" The days will need to be readjusted if the time that they awnser the swallowing question and the time that they do the evening diary is more than 30 minutes difference. If the difference from episode time to diary time is greater than 30 minutes then this episode will be considered to have happened on the previous day.

Total dysphagia episodes will be the sum of the real time events for the previous 14 days of the subjects scheduled visit date.

A dysphagia free day will be classified if there are no real time events and no recalled episodes. Total dysphagia free days will be calculated as the sum of the previous 14 days of the subject scheduled visit date.

16.2.1.6. Change from baseline in 7-day EEsAI total score at Weeks 12, 26 and 52 The total score for the Eosinophilic Esophagitis Activity Index (EEsAI) will be derived as follows from the five separate components, described in section 16.2.1.7.

Item	Categorized Result Score		
Frequency of trouble swallowing	Never	0	
	1-3 times/week	15	
	4-6 times/week	27	
	Daily	31	
Duration of trouble swallowing	≤5 minutes	0	
	>5 minutes	6	
Pain when swallowing	No	0	
	Yes	15	
VDQ score	0	0	

Document:

Author:

Version Number: 3.0

Version Date: 06NOV2019

Template No.: CS_TP_BS016 Revision 5 Reference: CS_WI_BS005

Page 40 of 70

Item	Categorized Result	Score
	>0 - 2.5	12
	>2.5 – 5.0	19
	>5.0 – 7.5	21
	7.5 – 10.0	23
AMS score	0 – 5.0	0
	>5.0 – 7.5	9
	>7.5 – 10.0	25
Total score		100

16.2.1.7. Change from baseline in 7-day EEsAI subscores at Weeks 12, 26 and 52

There are five subscores of the EEsAI:

- o Frequency of trouble swallowing
- o Duration of trouble swallowing
- o Pain when swallowing
- Visual Dysphagia Question (VDQ) score
- o Avoidance, Modification and Slow Eating (AMS) score

Subjects were asked whether they had, in the past 7 days, eaten the following types of food:

- o Solid meat (steak, chicken, turkey, lamb)
- o Soft foods (pudding, jelly, apple sauce)
- o Dry rice (grains don't stick) or sticky Asian rice (without sauce)
- o Ground meat (hamburger, meat loaf)
- o Fresh white untoasted bread or similar foods (donut, muffin, cake)
- Grits, porridge (oatmeal), rice pudding
- o Raw, fibrous foods, not grated (apple, carrot, celery)
- French fries without sauce or ketchup

Subjects were shown pictures of the 8 types of food and were asked to assess how difficult it would be to swallow

Author:

Version Number: 3.0

Version Date: 06NOV2019

Template No.: CS_TP_BS016 Revision 5 Reference: CS_WI_BS005

Page 41 of 70

each of them: The degree of perceived difficulties when eating a given food consistency will be scored as 0 for No difficulties, 1 for mild difficulties, 2 for moderate difficulties and 3 for severe difficulties. These scores for each food consistency were summed in the numerator of the score and divided by the maximum sum of grades that could be attained for each subject, which depends on the number of food consistencies consumed by a subject in a given recall period.

The VDQ score is derived as:

$$VDQ = \frac{(N1 \times 1) + (N2 \times 2) + (N3 \times 3)}{D \times 3} \times 10$$

Where:

- 1. N1 = number of food consistencies graded with 'Mild difficulties'
- 2. N2 = number of food consistencies graded with 'Moderate difficulties'
- 3. N3 = number of food consistencies graded with 'Severe difficulties'
- 4. D = number of relevant food consistencies for that subject

For the AMS score, answers to three items exploiting the pattern of behavioral adaptation were scored for each food consistency consumed by the subject. If patients recorded no behavioral changes, a score of 0 was assigned; when reporting eating slower than others, a score of 1 was assigned; when reporting the modification of certain food consistencies, a score of 2 was assigned; when reporting both eating slower than others and modifying certain food consistencies, a score of 3 was assigned; if the subject completely avoided one or several food consistencies due to EoE symptoms, a score of 5 was assigned. Scores for all consumed food consistencies were summed up in the numerator and divided by the maximum sum of scores that could be attained by a given subject.

The AMS score is derived as:

$$AMS = \frac{(N1 \times 1) + (N2 \times 2) + (N3 \times 3) + (N4 \times 5)}{D \times 5} \times 10$$

Where:

1. N1 = number of food consistencies with 'Yes' to 'Eating slowly' only

Author:

Version Number: 3.0

Version Date: 06NOV2019

Template No.: CS_TP_BS016 Revision 5 Reference: CS_WI_BS005

Page 42 of 70

- 2. N2 = number of food consistencies with 'Yes' to 'Modification' only
- 3. N3 = number of food consistencies with 'Yes' to both 'Eating slowly' and 'Modification'
- 4. N4 = number of food consistencies with 'Yes' to 'Avoidance' only
- 5. D = number of relevant food consistencies for that subject.

16.2.1.8. Subjects with 7-day EEsAI total score <20 at Weeks 12, 26 and 52

EEsAI total score will be derived as described in section 16.2.1.6.

